1 ADMINISTRATIVE INFORMATION

1.1 STUDY IDENTIFIERS

- Protocol: HREC/18/Alfred/42, version 5, dated 29th November 2023
- ClinicalTrials.gov register Identifier: NCT03737409
- Published protocol: [name], [name], [name], et al. Ambulatory oxygen for treatment of exertional hypoxaemia in pulmonary fibrosis (PFOX trial): a randomized controlled trial. *BMJ Open* 2020;10:e040798. doi:10.1136/bmjopen-2020-040798 (1)
- Funders: National Health and Medical Research Council (Australia) GNT 1139953, Swedish Society of Medicine (SLS-786791)

1.2 REVISION HISTORY

Version	Date	Changes made to document	Authors
1.0 (draft)	26 th April 2024	Initial draft	[name]
2.0 (draft)	18 th June 2024	Incorporated edits from [name]	[name], [name]
3.0 (final)	28 th June 2024	Incorporated edits from investigators	[name], [name]

2 STUDY SYNOPSIS

The PFOX trial is a prospective, parallel group, randomized, multi-centre international clinical trial examining the effects of ambulatory oxygen vs ambulatory air in people with fibrotic interstitial lung disease (ILD) and exertional desaturation. Written, informed consent is obtained for each participant. Participants are randomised 1:1 into two groups: (i) Oxygen Group: ambulatory oxygen therapy using a portable oxygen concentrator (POC) and (ii) Air Group: sham therapy using an identical POC. Randomisation is conducted via a secure web-based interface. Participants, health professionals and trial staff are blinded to the POC being used. Participants are followed up at 3 and 6 months.

2.1 STUDY OBJECTIVES

2.1.1 PRIMARY OBJECTIVE

The primary objective of PFOX is to determine whether ambulatory oxygen therapy delivered using a POC improves physical activity in daily life at 3 months when compared to ambulatory air in people with fibrotic ILD.

Primary hypothesis: Ambulatory oxygen therapy (compared to ambulatory air) improves physical activity in daily life, measured by the number of steps per day, at 3 months.

2.1.2 SECONDARY OBJECTIVES

Secondary objectives of PFOX are to determine the effect of ambulatory oxygen therapy delivered using a POC on functional exercise capacity, health-related quality of life (HRQL), breathlessness, fatigue, anxiety, depression, time spent in moderate to vigorous physical activity, sedentary time and oxygen saturation in daily life at 3 and 6 months in people with fibrotic ILD.

Secondary hypotheses:

Ambulatory oxygen therapy (compared to ambulatory air):

1. Improves functional exercise capacity at 3 and 6 months
2. Results in better HRQL at 3 and 6 months
3. Reduces symptoms of breathlessness and fatigue at 3 and 6 months
4. Reduces anxiety and depression at 3 and 6 months
5. Improves time spent in moderate to vigorous physical activity and reduces sedentary time at 3 and 6 months
6. Increases steps per day at 6 months

2.2 PATIENT POPULATION

2.2.1 INCLUSION CRITERIA

- aged 18 years and over
- have a physician-confirmed diagnosis of fibrotic ILD, such as IPF, connective tissue disease-associated ILD, fibrotic hypersensitivity pneumonitis, idiopathic non-specific interstitial pneumonia, unclassifiable idiopathic interstitial pneumonia, environmental/occupational lung disease or sarcoidosis, with features of diffuse fILD of >10% extent on high-resolution CT, with ILD being the predominant pathological process (2)
- have had stable pharmacotherapy over the previous 3 months
- exhibit exertional desaturation, defined as oxyhaemoglobin saturation (SpO_2) $\leq 88\%$ for at least 10 consecutive seconds during a 6-minute walk test (6MWT) performed on room air.

2.2.2 EXCLUSION CRITERIA

- Currently using or eligible for long-term oxygen therapy (LTOT), with eligibility defined as arterial oxygen pressure ≤ 55 mmHg at rest on room air, or 56–59 mm Hg with evidence of right heart failure
- current smokers, due to the risk of oxygen use near flames
- have predominantly obstructive lung disease, with forced expiratory ratio less than the lower limit of normal;
- pregnancy
- cognitively unable to consent
- currently participating in pulmonary rehabilitation
- non-ambulant
- have been admitted to an acute care hospital within the last 30 days
- death or transplant are anticipated within the study period.

OUTCOMES

2.2.3 PRIMARY OUTCOME

- Change from baseline in physical activity at 3 months, measured by the number of steps per day. Steps per day is measured using the StepWatch activity monitor (SAM) (Modus Health, Washington DC, USA). The SAM is worn on the ankle continuously for 7 days (except for bathing) at baseline, 3 months and 6 months. Days with < 8 hours recording or < 200 steps will be excluded. The mean number of steps per day will be calculated using the mean for all included days.

2.2.4 SECONDARY OUTCOMES

- Change from baseline in functional exercise capacity assessed by 6-minute walk distance at 3 and 6 months
- Change from baseline in health-related quality of life evaluated using the St George's Respiratory questionnaire at 3 and 6 months. Change in total score and domain scores will be reported.
- Change from baseline in health-related quality of life evaluated using the King's Brief Interstitial Lung Disease questionnaire at 3 and 6 months. Change in total score and domain scores will be reported.
- Change from baseline in dyspnea measured using the Dyspnea-12 questionnaire at 3 and 6 months. Change in total score and domain scores will be reported.
- Change from baseline in fatigue evaluated by the Fatigue Severity Scale at 3 and 6 months.
- Change from baseline in anxiety and depression measured by the Hospital Anxiety and Depression Scale at 3 and 6 months. Scores for anxiety and depression can vary from 0 to 21 and are stratified as follows: 0-7 (indicates absence of anxiety/depression symptoms); 8-10 (presence of symptoms of anxiety and depression in moderate degree - borderline); 11 or more (significant number of anxiety/depression symptoms - confirmed cases). Scores for anxiety and depression, as well as number of confirmed cases of anxiety and depression, will be reported.
- Change from baseline in time spent in moderate to vigorous physical activity, measured using the GeneActiv (GENEActiv, Cambridgeshire, a wrist-worn, triaxial accelerometer, at 3 and 6 months
- Change from baseline in sedentary time measured using the GeneActiv (GENEActiv, Cambridgeshire, a wrist-worn, triaxial accelerometer, at 3 and 6 months

2.2.5 SAFETY OUTCOMES

Adverse events are defined according to the Good Clinical Practice (GCP) guidelines including treatment emergent adverse events (TEAE's), which are undesirable events not present prior to medical treatment, or that worsens either in intensity or frequency following treatment. AEs of specific interest are:

- worsening of fILD (worsening of lung function, development of resting hypoxaemia)
- exacerbation of fILD

- burns (from smoking whilst using a POC, using the POC around an open flame or equipment that sparks)
- nosebleed or dry nose
- musculoskeletal injury from tripping on a POC
- bruising or infection at blood draw site
- fainting related to blood draw
- fainting, dizziness, chest pain, ataxic gait, lower limb pain or mental confusion related to 6-minute walk test
- hospitalization
- death.

2.2.6 TERTIARY OUTCOMES

- Use of oxygen therapy, downloaded from POC flash memory, measured in hours at 3 and 6 months
- Reason for cessation of therapy where relevant (patient request, commencement of LTOT, other).
- Oxygen saturation in daily life, measured using a Nonin 3150 Wrist Oximeter during waking hours for 2 consecutive days at 3 and 6 months.

2.3 INTERVENTION

For the oxygen group, ambulatory oxygen therapy will be delivered using the Inogen One G3 HF POC. Ambulatory air will be delivered using the Inogen One G3 HF POC that has been modified by the manufacturer to deliver only air. The POCs are identical in appearance.

All participants are informed that the aim of using a POC is to assist them to be more active, with fewer symptoms. They are encouraged to use the POC at all times when they are moving about, including walking at home or in the community, during exercise or during other activities. The POC should not be used when sitting still or sleeping. Written and verbal education are provided. Participants are encouraged to use their allocated POC during physical activity for the 6-month study period. The Inogen One G3 HF POC is used at its maximum flow setting of 5 for both groups.

2.4 RANDOMISATION AND BLINDING

Following baseline assessment participants are randomly allocated (1:1) to receive AOT or sham AOT (air) delivered by the Inogen One G3 HF POC. A computer generated, permuted block randomisation is used with stratification for (i) desaturation during 6MWT (<80% vs ≥80%) and (ii) site of recruitment. A remote, web-based, computer-generated randomisation procedure is used (provided by NHMRC Clinical Trials Centre).

Participants, clinicians and researchers will be blinded to group allocation. The Inogen One G3 HF POCs for AOT and air groups will be identical in appearance, display, weight and operation, with the only difference being the gas delivered. POCs were coded by the distributor, BOC, who have no involvement in trial conduct. All participants are advised against measuring oxygen saturation at home during the duration of the trial, as this does not represent usual clinical practice in any of the centres and may unblind the participants.

At the conclusion of the trial, participants are asked two questions to evaluate the success of blinding:

- Which treatment do you think you were receiving, oxygen or air?
- Did you have a pulse oximeter at home over the last 6 months? If yes, how did you use it?

2.5 SAMPLE SIZE

A total of 220 participants (110 per group) would provide 80% power to detect, at the two-sided 5% level, a clinically important difference between groups in the primary outcome of 599 steps per day (3). This assumes an SD of 1582 steps, based on physical activity data previously collected at our centre in 52 patients with fILD

(4). Previous experience suggests that 5% of participants could start LTOT (and cease POC use) over 6 months. We therefore intended to randomise 260 participants to ensure that 220 participants completed the study.

3 TRIAL REPORTING

The PFOX trial underwent important modifications because of the COVID-19 pandemic. We will report trial results according to the CONSERVE (CONSORT and SPIRIT Extension for RCTs Revised in Extenuating Circumstance) statement (5) as a framework to report the impact of the pandemic on PFOX and describe our mitigation approaches.

4 STATISTICAL ANALYSIS

4.1 GENERAL PRINCIPLES

- All outcomes and analyses are prospectively categorized as primary, secondary, or tertiary
- Summaries of continuous variables which are reasonably symmetrical will be presented as means and standard deviations, or as medians and inter-quartile ranges for skewed data. Categorical variables will be presented as frequencies and percentages.
- Differences in all endpoints between the two arms of the study will be tested independently at the two-tailed 0.05 level of significance. All estimates of treatment effects will be presented with 95% confidence intervals (CIs).
- Primary and secondary efficacy and safety outcomes analyses will be conducted on an intention-to-treat (ITT) basis so that all patients will be analysed in the group to which they were randomized irrespective of whether or not they received the allocated treatment.
- The ITT analysis strategy for PFOX is defined as follows:
 - Is based on an ITT design that aims to collect all outcome data on all randomized subjects;
 - Includes a main analysis that keeps subjects in their randomized groups, analyses all available outcome data, and is valid under a named plausible assumption about the missing data;
 - Includes sensitivity analyses that consider a range of plausible alternative assumptions that differ from the main assumption about the missing data;
 - All individuals are included in sensitivity analyses.
- For primary and secondary analyses, the treatment effect on the primary efficacy outcome will be adjusted for the baseline measurement of the outcome.
- Subgroup analyses will be carried out irrespective of whether there is a significant treatment effect on the primary outcome. Their purpose is to supplement evidence from the primary analysis to help to fully characterise the treatment effect. Results from subgroup analyses will be interpreted in this context.
- Analyses will be conducted primarily using R statistical software.

4.2 INTERIM ANALYSES

There are no formal interim analyses specified for this trial. The DSMB periodically review group data for the primary outcome measure and the major subsidiary analyses, including the safety analyses.

4.3 PARTICIPANT DISPOSITION

Flow of patients through the study will be displayed in a standard CONSORT diagram. The report will include the number of screened patients who met the inclusion criteria, the number included, and the major reasons for exclusion of eligible patients. At follow up, the number of patients included, withdrawn, lost to follow up and the number who died within that period will also be reported.

4.4 MULTIPLICITY ADJUSTMENT

No formal adjustments will be undertaken to constrain the overall type I error associated with the secondary, tertiary, and exploratory analyses. Their purpose is to supplement evidence from the primary analysis to more fully characterise the treatment effect. Results from the secondary and tertiary analyses will be interpreted in this context.

4.5 BLIND REVIEW

The persons responsible for developing this statistical analysis plan will be kept blind until after the plan has been signed off, trial close-out is complete, and data lock is done. The results will not be unblinded to the rest of the study team until the final statistical report has been completed.

4.6 DATA SETS TO BE ANALYSED

All data will be analysed by intention to treat, including all randomised participants in the groups to which they were allocated, regardless of adherence.

4.7 PATIENT CHARACTERISTICS AND BASELINE COMPARISONS

In order to assess balance, description of the specified baseline characteristics will be presented for the Oxygen and Air groups (Table 1). Discrete variables will be summarized as frequencies and percentages. Unless otherwise indicated in the tables percentages will be calculated according to the number of patients for whom data are available. Continuous variables will be summarized by use of either mean and standard deviation or median and interquartile range. Durations and time intervals will be summarized by medians, IQRs, and ranges.

Baseline measures for patients will be presented by group for the following variables:

age, gender, body mass index, type of fibrosing ILD, respiratory function (FEV1, FVC and TLCO, absolute and %predicted), 6-minute walk distance (metres), resting SpO₂, nadir SpO₂ on 6MWT (%), % of waking hours with SpO₂ ≤ 88% during daily life, physical activity (average steps/day), Dyspnoea-12, KBILD, Hospital Anxiety and Depression Scale.

4.8 CONCOMITANT THERAPIES

The number of participants in each group who commence LTOT will be reported and compared across randomised arms. The number of participants in each group who commence new pharmacotherapies and their nature will be reported. Outcome data for participants who commence LTOT or new pharmacotherapies will be analysed according to allocated treatment group, as per intention to treat principles.

4.9 ANALYSIS OF THE PRIMARY OUTCOME

The primary outcome is change from baseline in physical activity at 3 and 6 months, measured as steps/day using the Stepwatch Activity Monitor.

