4.9.1 MAIN ANALYSIS

The primary analysis will use linear mixed models, with site as a random effect. We will compare change from baseline at 3 and 6 months between groups, with the baseline measurement included in the model as a covariate. The treatment effect will be presented as the mean difference between groups with the corresponding 95% confidence interval. Desaturation during 6MWT, although a stratifying factor in the design, will be modelled as a fixed effect.

The assumption of homogeneity of variance will be examined for each outcome by plotting residuals from the model against fitted values. Where right skewness results in heterogeneity of variance, a log transformation will be applied.

Missing data are anticipated for the primary outcome. The primary outcome is assumed to be missing-at-random (MAR), i.e. it is assumed that the probability of 3 month steps/day data being missing may depend on the values of the observed data, but not on the values of the missing data. Important explanatory and auxiliary variables such as age, type of ILD, respiratory function and extent of exertional desaturation are being collected and will be examined to assess the plausibility of the MAR assumption.

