4.10 ANALYSIS OF SECONDARY OUTCOMES

Changes in secondary outcomes listed in 2.2.4 will be compared between groups using linear mixed models, using the same random and fixed factors as for the primary outcome, including the baseline measure of the outcome as a covariate.

- 4.10.1 Change in functional exercise capacity assessed by 6-minute walk distance
- 4.10.2 Change in health-related quality of life evaluated using the St George's Respiratory Questionnaire
- 4.10.3 Change in health-related quality of life evaluated using the K-BILD Questionnaire
- 4.10.4 Change in dyspnea measured using the Dyspnea-12 questionnaire
- 4.10.5 Changes in fatigue evaluated by the Fatigue Severity Scale
- 4.10.6 Change in anxiety and depression measured by the Hospital Anxiety and Depression Scale
- 4.10.7 Change in time spent in moderate to vigorous physical activity
- 4.10.8 Change in sedentary time

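### The SAP gives two definitions of the primary outcome (steps/day at 3 months, or at 3 and 6 months) and does not name the contrast that decides the trial

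*SAP*

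**What the plan says.** Section 2 is consistent on the time point:

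- The primary hypothesis in 2.1.1 is that ambulatory oxygen "improves physical activity in daily life, measured by the number of steps per day, at 3 months".
- Section 2.2.3 defines the primary outcome as "Change from baseline in physical activity at 3 months, measured by the number of steps per day".
- Section 2.1.2 lists as secondary hypothesis 6: "Increases steps per day at 6 months".

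Section 4.9 opens the primary analysis differently: "The primary outcome is change from baseline in physical activity at 3 and 6 months". Section 4.9.1 continues: "We will compare change from baseline at 3 and 6 months between groups". It then presents one treatment effect as a mean difference with a 95% confidence interval and gives no time point for it. Its missing-data paragraph goes back to 3 months, stating the missing-at-random assumption for "the probability of 3 month steps/day data being missing".

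For secondary outcomes, section 4.10 says: "Changes in secondary outcomes listed in 2.2.4 will be compared between groups using linear mixed models". The list in 2.2.4 does not include steps/day at 6 months.

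On error control, section 4.1 says: "Differences in all endpoints between the two arms of the study will be tested independently at the two-tailed 0.05 level of significance". Section 4.4 waives adjustment for secondary, tertiary and exploratory analyses and has no rule for two primary time points.

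**The concern.** The same 6-month measurement is secondary in section 2 and part of the primary outcome in section 4. Because it is absent from 2.2.4, and therefore from 4.10, its only place in the analysis section is under the primary outcome.

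Modelling both visits together is not a fault. The fault is that 4.9.1 does not say which estimate from that model decides the trial: the 3-month difference, the 6-month difference, both, or an effect pooled over visits. No treatment-by-visit term is named that would settle it. The subgroup analyses in 4.9.2 add an interaction to the same main model for the primary outcome, so they inherit the ambiguity.

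If the results at 3 and 6 months differ, sections 2 and 4 would support different headline conclusions, and the choice could be made after the data are seen. The readings also differ in type I error, in power or in the question answered.

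**Working it through.** **Inputs from the SAP.** Difference 599 steps/day, SD 1582, 110 per group, two-sided 5%, 80% power (section 2.5); each endpoint tested at two-sided 0.05 (section 4.1).

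**Inputs assumed.** The SAP gives no correlation ρ between the 3- and 6-month treatment estimates. I take ρ = 0.5, 0.7 and 0.8, with ρ = 0 as the independent limit, and equal precision at both visits.

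**Step 1: reproduce the plan's figure.** The expected test statistic is 599 / (1582 × √(2/110)) = 599 / 213.3 = 2.808. Power is Φ(2.808 − 1.960) = Φ(0.848) = 0.802. The usual formula returns 110 per group, 220 in total, as stated. The calculation therefore corresponds to one test of one difference.

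**Step 2: compare the readings.** Treat the two test statistics (3 and 6 months) as bivariate normal with correlation ρ and critical value 1.960.

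- *Either time suffices.* Type I error is the probability that at least one |Z| exceeds 1.960 when there is no effect at either time. With ρ = 0 it is 1 − 0.95² = 0.0975.
- *Both required.* Type I error with no effect at either time is 0.05 + 0.05 minus the either-time figure; for ρ = 0.5, 0.10 − 0.0907 = 0.0093. Power is the probability that both statistics exceed 1.960 when each has mean 2.808.
- *Pooled, equal weights.* With no effect at 3 months and 599 steps at 6 months, the pooled statistic has mean (2.808/2) / √((1 + ρ)/2). For ρ = 0.5 this is 1.404/0.866 = 1.621, and the rejection probability is about Φ(1.621 − 1.960) = 0.37.

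| Reading | ρ = 0 | ρ = 0.5 | ρ = 0.7 | ρ = 0.8 |
|---|---|---|---|---|
| 3 months only: type I error | 5% | 5% | 5% | 5% |
| 3 months only: power | 80.2% | 80.2% | 80.2% | 80.2% |
| Either suffices: type I error | 9.75% | 9.1% | 8.3% | 7.8% |
| Both required: type I error, no effect at either time | 0.25% | 0.9% | 1.7% | 2.2% |
| Both required: power, 599 steps at each time | 64.3% | 69.0% | 71.5% | 73.1% |
| Pooled: positive with 0 at 3 months, 599 at 6 months | 51% | 37% | 33% | 32% |

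In the last scenario the 3-month contrast would be positive with probability 5%. The pooled test keeps its 5% error when there is no effect at either time, but it answers a different question from the primary hypothesis in 2.1.1.

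**The case against.** The strongest reply is that 4.9 contains a drafting slip. The SAP states one primary hypothesis, at 3 months; its outcome definition says 3 months; 6-month steps/day is expressly a secondary hypothesis; and 4.9.1 itself links the primary outcome to 3-month data. The SAP also uses the term primary outcome as a name for the variable steps/day, in section 4.12.4 and in the figure list of Appendix 1, so 4.9 may only mean that steps/day is modelled at both visits. A claim of primary success at 6 months alone would contradict section 2.

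Much of this stands. Three months is the likely intention, and the SAP nowhere says that either time suffices, that both are required, or that a pooled effect decides. The figures above therefore show what each open reading would do; they are not the error rate or power of an agreed plan. They also rest on an assumed correlation, equal precision at both visits and an unadjusted two-sample calculation, whereas the planned model adjusts for baseline. The missing list entry in 2.2.4 is minor on its own, since 6-month steps/day is still measured and modelled.

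The objection does not remove the contradiction. Section 4.9 is the text an analyst will implement, it assigns 6 months to the primary outcome, and the effect reported in 4.9.1 has no time point. The protocol was not available for this review, but the conflict lies within the SAP. That it is probably a slip makes it easy to correct; it is no reason to leave the primary endpoint stated in two ways.

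**Conclusion.** The concern holds. The SAP defines its primary outcome in two incompatible ways and does not identify the deciding contrast. This should be corrected before unblinding, because it determines which test decides the trial.

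The contradiction itself needs no assumptions. Its numerical consequence depends on the reading and on the assumed correlation of 0.5 to 0.8: a type I error of up to 9.1% if either time sufficed, a loss of about 7 to 11 percentage points of power if both were required (80.2% down to 73.1% or 69.0%), or a changed question if a pooled effect were used. Under the 3-month reading of section 2, the error rate is 5%, power is 80.2%, and the sample size needs no change on this account.

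**What to change.** Before unblinding:

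- In 4.9, define the primary outcome as the change in steps/day from baseline to 3 months, in line with 2.1.1 and 2.2.3.
- In 4.9.1, name the oxygen-minus-air difference at 3 months, taken from the mixed model with a treatment-by-visit term, as the single primary contrast, tested once at two-sided 0.05. State that no effect pooled over 3 and 6 months serves as the primary result. This last statement is strictly redundant once the contrast is named, but it closes the remaining reading.
- In 2.2.4 and 4.10, list the change in steps/day at 6 months as a secondary outcome, estimated from the same model.
- In 4.9.2, let the subgroup interactions refer to the 3-month contrast.

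The cost is SAP wording only. Data collection, the joint model of both visits and the sample size stay as they are. The sponsor gives up any claim of primary success on the 6-month result alone, which the hypotheses in section 2 do not support in any case.

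### Section 4.9 sets the primary outcome at 3 and 6 months, against 3 months in 2.1.1 and 2.2.3, and 4.9.1 names no primary contrast

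*SAP*

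**What the plan says.** The SAP places the primary outcome in time in several sections, and they do not agree.

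- **2.1.1, primary objective:** whether ambulatory oxygen "improves physical activity in daily life at 3 months when compared to ambulatory air". The primary hypothesis in the same section also names 3 months.
- **2.2.3, primary outcome:** "Change from baseline in physical activity at 3 months, measured by the number of steps per day".
- **2.1.2, secondary hypothesis 6:** "Increases steps per day at 6 months".
- **4.9, analysis of the primary outcome:** "The primary outcome is change from baseline in physical activity at 3 and 6 months".
- **4.9.1, main analysis:** "We will compare change from baseline at 3 and 6 months between groups". The result is to be presented as a single mean difference with its 95% confidence interval, and no visit is attached to it.

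On the model, 4.9.1 says: "The primary analysis will use linear mixed models, with site as a random effect". It adds the baseline value as a covariate and desaturation on the walk test as a fixed effect. It does not mention visit, treatment by visit or a within-participant term, and does not say whether the two visits share a model. Section 4.10 carries the same factors over to every secondary outcome.

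On error control, 4.1 says: "Differences in all endpoints between the two arms of the study will be tested independently at the two-tailed 0.05 level of significance". Section 4.4 waives adjustment for secondary, tertiary and exploratory analyses and does not mention more than one primary comparison.

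**The concern.** The section that tells the analyst what to do departs from the section that defines the outcome. Under 2.1.2 the 6-month comparison of steps is secondary; under 4.9 it is part of the primary outcome. Both cannot hold, and 4.9.1 does not settle it.

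What is at stake is the meaning of the primary result. With 3 months as the sole primary visit, there is one test at 5%. With both visits primary, there are two tests at 5% each, the waiver in 4.4 does not cover them, and no rule says what counts as success. If the results differ between visits, either could be presented as the primary finding with support from some part of the plan.

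The unstated fit is a smaller, related gap. Separate models per visit and one joint model with a visit structure are both compatible with the text. The singular mean difference does not say which contrast it refers to.

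**Working it through.** **Step 1. Set the sections side by side.**

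| SAP section | Visit for the primary outcome |
|---|---|
| 2.1.1 objective and hypothesis | 3 months |
| 2.2.3 outcome definition | 3 months |
| 2.1.2 hypothesis 6 | 6-month steps is secondary |
| 2.5 sample size | one comparison, visit not named |
| 4.9 | 3 and 6 months |
| 4.9.1 comparison | 3 and 6 months, neither named as primary |
| 4.9.1 missing-data statement | 3 months |

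The missing-data statement reads: "it is assumed that the probability of 3 month steps/day data being missing may depend on the values of the observed data". It indicates which visit the authors had in mind, but it concerns missingness and does not select a contrast.

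**Step 2. Reproduce the plan's sample size.** Inputs from 2.5: difference 599 steps, SD 1582, two-sided 5%, 80% power, equal groups.

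n per arm = 2 × 1582² × (1.960 + 0.842)² / 599² = 109.5, rounded up to 110, or 220 in total. This agrees with the SAP.

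Power with 110 per arm: SE = 1582 × √(2/110) = 213.3, and Φ(599/213.3 − 1.96) = Φ(0.848) = 0.802.

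The calculation is for one contrast with no alpha split, which fits the definition in 2.2.3. Section 2.5 does not say that 1582 is the SD of a change score or of a baseline-adjusted residual. This step therefore only checks the plan's own figure; the type I errors below do not use the SD.

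**Step 3. Size if 2.2.3 governs.** One 3-month contrast at two-sided 0.05 has a type I error of about 5%. The primary test is not harmed.

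**Step 4. Size if 4.9 is taken literally.** There are two primary tests, each at 0.05. Let Z₃ and Z₆ be the two test statistics, standard bivariate normal under the null with correlation ρ. The chance that at least one is significant is

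1 − P(|Z₃| ≤ 1.96 and |Z₆| ≤ 1.96).

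The SAP gives no value for ρ. Two outcomes measured in the same participants three months apart should be positively correlated, and the range 0.3 to 0.8 is an assumption.

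| ρ (assumed) | Type I error, success at either visit |
|---|---|
| 0.3 | 9.5% |
| 0.5 | 9.1% |
| 0.7 | 8.4% |
| 0.8 | 7.8% |

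For reference, independence would give 1 − 0.95² = 9.75%.

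**Step 5. Where is 6-month steps analysed?** The secondary outcomes in 2.2.4 do not include steps at 6 months, and 4.10 analyses only that list. The analysis of 6-month steps therefore appears only under the primary-outcome heading. This may explain how the wording of 4.9 arose, and it shows that 2.2.4 needs an entry.

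**The case against.** The strongest reply is that the plan largely settles the matter. The objective, the hypothesis, the outcome definition, the missing-data statement and a sample size built on one comparison all fit 3 months, and 6-month steps is listed as a secondary hypothesis. Since 4.9 is the only place where 6-month steps gets an analysis, its wording may be loose drafting that covers both visits under one heading. On that reading the primary test has its planned size and power, and the 6-month result falls under the declared no-adjustment policy in 4.4.

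Most of this stands. It makes 3 months the likelier intention and the inflated error rate conditional. It does not remove the contradiction: 4.9 states a definition of the primary outcome, 4.9.1 repeats the two visits, and no sentence says which section prevails.

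A reader might infer more, in two ways the document does not support.

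- **That both visits must succeed, so power falls short of 80%.** No section states such a rule, and 4.1 has each endpoint tested on its own.
- **That both visits will be pooled into one effect as if a participant's two values were independent, because site is the only random effect named.** The text does not exclude visit or participant terms and nowhere proposes averaging visits. It speaks of models in the plural, and Appendix 1 plans a longitudinal plot of means. Separate models per visit are the more natural reading.

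Preferring a joint repeated-measures model to separate models is partly a matter of taste. The objection is that the plan does not say which is used.

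**Conclusion.** Wrong as written, and it should be fixed. Section 4.9 contradicts 2.1.1, 2.1.2 and 2.2.3 on the primary visit, and 4.9.1 leaves both the primary contrast and the handling of the two visits open.

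The size depends on which section governs. If 2.2.3 does, as most of the plan suggests, the type I error stays at about 5% and the sample size is right as it stands. If 4.9 does, success at either visit carries a type I error of about 7.8% to 9.5%. That range rests on each visit being tested at two-sided 0.05, success at either visit being claimed, and a between-visit correlation of 0.8 to 0.3, which is assumed.

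The finding is not that the sample size is wrong, nor that the planned model necessarily gives invalid intervals.

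**What to change.** 1. In 4.9, word the primary outcome as change from baseline in steps per day at 3 months, in line with 2.2.3.
2. In 4.9.1, name the 3-month treatment difference as the sole primary test at two-sided 0.05 and the 6-month difference as secondary. Report each with its own mean difference and 95% confidence interval.
3. Add change in steps per day at 6 months to the secondary outcomes in 2.2.4, so that it matches hypothesis 6 in 2.1.2.
4. State whether the visits are fitted in separate models or jointly. If separately, name the 3-month model as the primary one. If jointly, include visit, treatment by visit, and a participant random effect or within-participant covariance, alongside the baseline, desaturation and site terms already given.
5. Use the same structure in 4.10.

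The cost is a phrase in 4.9, a few sentences in 4.9.1 and one line in 2.2.4. The sample size of 220, the 5% level and the planned power do not change, and no further data are needed.
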